This study aims to identify the RP2D and preferred dosing schedule of RP-6306 in combination with FOLFIRI. The DLT evaluation period will consist of 2 cycles (28 days) of treatment. Initially, RP-6306 will be given on a continuous, once daily (QD) schedule (Module 1a) with dose escalation and de-escalation decisions guided by the BOIN drug combination criteria. If necessary, an intermittent dosing schedule (Module 1b) of 3 consecutive days on / 4 consecutive days off may be explored, and Module 1a may be terminated or proceed concurrently with Module 1b. Escalation/de-escalation will proceed independently as guided by the BOIN drug combination criteria. If both modules are run concurrently, patients will be enrolled into either Module 1a or 1b based on available slot openings at the time of signing the ICF and allocated to a cohort by the Medical Monitor with guidance from the SRC.

Module 1a:

The study will start at Dose Level 1 with up to 2 patients receiving 40 mg QD, oral RP-6306 in combination with 180 mg/m² IV irinotecan given over 30 to 90 minutes, 400 mg/m² IV leucovorin given over 30 to 90 minutes with irinotecan, and 400 mg/m² IV fluorouracil bolus after leucovorin, then 2400 mg/m² IV continuous IV of fluorouracil over 46 hours (Days 1 and 2) of each 14-day cycle.

This dose of RP-6306 was chosen based on the observed tolerability and PK of RP-6306 monotherapy in the MYTHIC study. If Dose Level 1 is tolerated, the dose of RP-6306 will be escalated to 120 mg and the dose of irinotecan will be maintained at 180 mg/m² daily (Dose level 2). In addition, patients treated at Dose Level 1 will be eligible to receive RP-6306 at 120 mg QD, if Dose Level 2 has completed the DLT evaluation period and if agreed upon by the SRC. If Dose Level 1 is not tolerated, the dose of irinotecan will be de-escalated to 150 mg/m² and RP-6306 will be maintained at 40 mg daily (Dose level 1D).

After Dose Level 2, dose escalation of RP-6306 will proceed to the next higher dose level following BOIN criteria and dose escalation and de-escalation rules as follows:

- Dose escalation will progress with N≥2 patients with increases of up to 100% RP-6306 until a
 DLT is observed (Level R in Figure B and Table A below). Dose decisions will depend on 2 or
 more evaluable patients completing the first 2 14-day treatment cycles.

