- For de-escalation at Level R and thereafter, the next dose level of RP-6306 will be ≥25% lower than the current dose (rounded down based on capsule strength) or de-escalated down to the highest previously tolerated dose based on review of the toxicity patterns by the SRC. In addition to decreasing the daily dose level of RP-6306, de-escalation can involve a reduced frequency of dosing (eg, 3 consecutive days on / 4 consecutive days off or 1 week on / 1 week off).
- Dose escalation of RP-6306 will follow the BOIN criteria as guided by the SRC. RP-6306 can continue with increases of 20% to 50% (R+1).

Intrapatient dose escalation may progress in subsequent patients once the next dose level is cleared by the SRC and the treating physician and the patient agrees that intrapatient dose escalation is desired.

Module 1b:

If tolerability of continuous RP-6306 with FOLFIRI is limiting, Module 1b will be initiated if agreed upon by the SRC. In Module 1b, an intermittent dosing schedule of RP-6306 given 3 consecutive days on / 4 consecutive days off will be tested in combination with FOLFIRI. When Module 1b is initiated, the starting dose of RP-6306 and FOLFIRI will be the same as the highest total daily dose evaluated in Module 1a and will be given to a cohort of N≥2 patients. To allow better dose and schedule exploration early in the development, additional schedules may be evaluated that involve intermittent dosing (eg, 2 consecutive days on / 5 consecutive days off or 1 week on / 1 week off) depending on observed toxicities. The dose of RP-6306 or FOLFIRI will be increased or decreased per BOIN criteria independently of Module 1a until an MTD is established. Dose escalation decisions will be discussed with the SRC after at least 2 evaluable patients completing the first 2 14-day treatment cycles and based on the emerging safety and tolerability profile, and clinical PK/pharmacodynamic data across the entire patient population in Modules 1a and 1b.

In the event Modules 1a and 1b are explored concurrently, the Medical Monitor and SRC will prioritize slot allocation for each module. The highest dose level of RP-6306 in this study will not exceed the MTD of RP-6306 monotherapy identified in the MYTHIC study for a given schedule. The totality of safety, PK, pharmacodynamic, and preliminary efficacy data will be used to select a preferred RP2D and schedule for RP-6306 and FOLFIRI.

QD=once daily.

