	IV over 30-90 min	Irinotecan	150 mg/m^2	120 mg/m^2	120 mg/m^2	
FOLFIRI once every 2 weeks on Day 1 ^d	IV over 30-90 min concurrently with irinotecan	Leucovorin	400 mg/m^2	400 mg/m^2	400 mg/m^2	
	IV bolus after leucovorin	Fluorouracil	400 mg/m^2	400 mg/m^2	No bolus	
		THEN	ek.			
	IV continuous infusion; start on Day 1 over 46 hours only	Fluorouracil	2400 mg/m^2	2400 mg/m ²	2400 mg/m ²	

BOIN=Bayesian optimal interval, DLT=dose-limiting toxicity, min=minute(s); MTD=maximum tolerated dose; MYTHIC=Phase 1 dose escalation study of RP-6306 monotherapy; N=any dose level after R+1; R=dose level at which DLT is observed; SRC= Safety Review Committee.

^a Modules 1a and 1b will progress independently

^b Level 1 or 2 may be Level R if early treatment-related toxicity is observed

^c The order of escalation (RP-6306 or irinotecan in the FOLFIRI regimen) will be guided by BOIN drug combination criteria and agreed upon by the SRC.

^d Investigators that would like to hold or modify the administration of the fluorouracil bolus and/or leucovorin require approval by the Repare Medical Monitor to do so.

(A2) Dosing Regimens for Module 1	(Intermittent RP-6306, 3 Consecutive)	Days On / 4 Consecutive Days Off) ^a
-----------------------------------	--	--

Treatment Frequency	Drug	Route of Administration	Dose Level R+1 ^c	Dose Level R+N°		
Once Daily	RP-6306	Oral	Per BOIN rules up to 100% increase or MTD in MYTHIC	Per BOIN rules up to 100% increase or MTD in MYTHIC		
	Irinotecan	IV over 30-90 min	Up to 180 mg/m^2	Up to 180 mg/m^2		
FOLFIRI once	Leucovorin	IV over 30-90 min concurrently with irinotecan	400 mg/m ²	400 mg/m^2		
every 2 weeks	Fluorouracil	IV bolus after leucovorin	400 mg/m^2	400 mg/m^2		
on Day 1 ^d	THEN					
	Fluorouracil	IV continuous infusion; start on Day 1 over 46 hours only	2400 mg/m ²	2400 mg/m ²		

*If Dose Level 1 is not tolerated

Treatment Frequency	Route of Administration	Drug	Dose Level 1D ^c	Dose Level 2D ^c	Dose Level 3Dc
Once Daily	Oral	RP-6306	40 mg	40 mg	40 mg
	IV over 30-90 min	Irinotecan	150 mg/m^2	120 mg/m^2	120 mg/m ²
FOI FIDI	IV over 30-90 min concurrently with irinotecan	Leucovorin	400 mg/m^2	400 mg/m^2	400 mg/m^2
FOLFIRI once every 2 weeks	IV bolus after leucovorin	Fluorouracil	400 mg/m^2	400 mg/m^2	No bolus
on Day 1 ^d		THEN	×		50:
Lad opening the State of the St	IV continuous infusion; start on Day 1 over 46 hours only	Fluorouracil	2400 mg/m ²	2400 mg/m ²	2400 mg/m ²

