BOIN=Bayesian optimal interval; DLT=dose-limiting toxicity; IV=intravenous; min=minute(s); MTD=maximum tolerated dose; MYTHIC=Phase 1 dose escalation study of RP-6306 monotherapy; N=any dose level after R+1; R=dose level at which DLT is observed; SRC= Safety Review Committee.

^a Modules 1a and 1b will progress independently.

^b Level 1 or 2 may be Level R if early treatment-related toxicity is observed.

^c The order of escalation (RP-6306 or irinotecan in the FOLFIRI regimen) will be guided by BOIN drug combination criteria and agreed upon by the SRC.

^d Investigators that would like to hold or modify the administration of the fluorouracil bolus and/or leucovorin require approval by the Repare Medical Monitor to do so.

If Dose Level 1 is not tolerated in Module 1a, Dose Level 1D will be explored. At Dose Level 1D, RP-6306 will be given at 40 mg daily on a continuous schedule and irinotecan in the FOLFIRI regimen will be reduced to 150 mg/m² over 30 to 90 minutes on Day 1 of each 14-day cycle. If Dose Level 1D is tolerated and deemed safe by the SRC, irinotecan will be maintained at 150 mg/m², and escalation of RP-6306 will proceed in increments of 50% to 100% in a continuous schedule. If Dose Level 1D is not tolerated, Dose Level 2D will be explored. At Dose Level 2D, RP-6306 will be given at 40 mg daily on a continuous schedule and irinotecan in the FOLFIRI regimen will be reduced to 120 mg/m² over 30 to 90 minutes on Day 1 of each 14-day cycle. If Dose Level 2D is tolerated and deemed safe by the SRC, irinotecan will be maintained at 120 mg/m² and escalation of RP-6306 will proceed in increments of 50% to 100% in a continuous schedule. If dose level 2D is not tolerated, dose Level 3D will be explored, in which the bolus of fluorouracil will be eliminated from the regimen.

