Based on the outcome of RP-6306 PK evaluation in the initial dose levels and emerging PK data in the MYTHIC (RP-6306-01) monotherapy study, a consideration for a twice daily (BID; same total daily dose as QD) RP-6306 administration will be discussed with the SRC. The decision to initiate BID dosing will be based on observed patient outcomes (eg, absence of toxicities, tumor response, or other pharmacologic activity) and PK parameters such as, but not limited to, elimination half-life ($t_{1/2}$) is <12 hours or the C_{max} : C_{min} ratio >10 (where C_{min} is the minimum observed plasma concentration within the dosing interval). The same dose escalation/de-escalation criteria will apply for BID dosing cohorts. If BID dosing is initiated, the SRC can elect to continue enrolling patients on a daily dosing arm or cease enrollment on this arm based on the data collected.

Maximum Tolerated Dose:

The BOIN design will be employed to find the MTD of continuous RP-6306 (Module 1a) and, if necessary, intermittent RP-6306 (Module 1b) in combination with FOLFIRI. The target toxicity rate is 25%. The maximum sample size will be 80 patients for dose finding in Modules 1a and 1b combined. DLTs occurring within the first 28-days (2 cycles) will be used to direct MTD finding.

The BOIN design uses the following criteria, optimized to minimize the probability of incorrect dose assignment, to guide dose escalation/de-escalation:

- If the observed DLT rate at the current dose is ≤0.197 (<20%), escalate the dose to 1 of the 2 next higher dose levels (ie, 1 level increase of RP-6306 or 1 level increase of FOLFIRI).
- If the observed DLT rate at the current dose is ≥ 0.298 ($\ge 30\%$), de-escalate the dose to 1 of the 2 next lower dose levels (ie, 1 level decrease of RP-6306 or 1 level decrease of FOLFIRI).
- Otherwise, stay at the current dose.

With the BOIN design, re-escalation after de-escalation is allowed and it is possible to escalate back to a dose level previously declared nontolerated. Prior to re-escalating to a previously nontolerated dose, an intermediate dose level may be explored. The final decision regarding degree of re-escalation will be determined by the SRC based on the totality of the safety and PK data.

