For the purpose of overdose control, doses j and higher levels will be eliminated from further consideration if $Pr(pj > 0.25 \mid data) > 0.95$ and at least 3 evaluable patients have been treated at dose level j, where pj is the true DLT rate of dose level j, j = 1, ..., 5. This posterior probability is evaluated based on the beta-binomial model yj | pj ~ binomial(pj) with pj ~ uniform(0, 1), where yj is the number of patients experienced DLT at dose level j. When the lowest dose is eliminated, stop the trial for

safety. When the lowest dose is eliminated, stop the trial for safety. The above dose escalation/de-escalation and elimination rule can be equivalently presented in Table B, which will be used to conduct the trial.

Table B provides information on the different dose decisions based on number of evaluable patients and the number of DLTs reported. Note, more than 6 patients may be exposed at a dose level to better define the MTD.

 Table B:
 Dose Escalation/De-escalation Rules for the BOIN Design

		Number of Evaluable Patients at Current Dose Level										
Action	1	2	3	4	5	6	7	8	9	10	11	12
↑ if number of DLT ≤	0	0	0	0	0	1	1	1	1	1	2	2
Stay current dose if number of DLT =	NA	NA	NA	1	1	NA	2	2	2	2	3	3
\downarrow if number of DLT \geq	1	1	1	2	2	2	3	3	3	3	4	4
Elim if number of DLT ≥	NA	NA	3	3	3	4	4	4	5	5	6	6

BOIN = Bayesian optimal interval; \(\geq = \text{increase}, \quad = \text{decrease}, \text{DLT} = \text{dose-limiting toxicity}, \\ \text{Elim=eliminate}, \text{NA} = \text{not applicable}, \text{dose cannot be eliminated until at least 3 patients have been treated}

Note: Number of DLT is the number of patients with at least 1 DLT. When none of the actions (ie, escalate, de-escalate or eliminate) is triggered, stay at the current dose for treating the next cohort of patients.

Dose finding starts at Dose Level 1. The steps to implement the BOIN design are described as follows:

- 1. Patients in the first cohort are treated at Dose Level 1. Dose decisions will depend on 2 or more evaluable patients completing the first 2 14-day treatment cycles.
- 2. To assign a dose to the next cohort of patients, conduct dose escalation/de-escalation according to the rule displayed in Table B. When using Table B, please note the following:
 - a. "Eliminate" means eliminate the current and higher doses from the trial to prevent treating any future patients at these doses because they are overly toxic.

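### The elimination and MTD rules assume one complete dose order, which combinations such as RP-6306 40 mg with irinotecan 180 mg/m² and 80 mg with 150 mg/m² do not have

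*Protocol*

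**What the plan says.** Combinations are written below as RP-6306 mg / irinotecan mg/m².

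**How two-drug combinations arise.** The Protocol Synopsis (Dose Finding, Module 1a) and SAP 3.2.1 start at 40/180 and then raise RP-6306. For a step down, "the next dose level of RP-6306 will be ≥25% lower than the current dose (rounded down based on capsule strength"), or the dose is "de-escalated down to the highest previously tolerated dose based on review of the toxicity patterns by the SRC". The general rule (Synopsis, Maximum Tolerated Dose; SAP 3.2.2) allows a step in either drug: "de-escalate the dose to 1 of the 2 next lower dose levels (ie, 1 level decrease of RP-6306 or 1 level decrease of FOLFIRI"). If 40/180 is not tolerated, Dose Level 1D (40/150) follows. If that is tolerated, "irinotecan will be maintained at 150 mg/m², and escalation of RP-6306 will proceed in increments of 50% to 100"%. The 120 mg/m² level has the same script. Footnote c to the dose tables adds: "The order of escalation (RP-6306 or irinotecan in the FOLFIRI regimen) will be guided by BOIN drug combination criteria", with Safety Review Committee (SRC) agreement. In Module 1b, too, either RP-6306 or FOLFIRI may be moved.

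**How the rules treat the levels.** In the Protocol's overdose control, "doses j and higher levels will be eliminated from further consideration", where "pj is the true DLT rate of dose level j, j = 1, ..., 5". Step 2a in both documents likewise removes the current dose and those above it. The MTD is the dose whose isotonic estimate is closest to, and not above, 30% (Synopsis; SAP 3.2.2). SAP section 7 takes the highest dose with a DLT rate below 25% and refers to pooled adjacent violators. Neither document says what counts as higher when one drug is up and the other is down.

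**The concern.** A single index, an instruction to remove higher levels and a pooled-adjacent-violators fit all need every pair of levels to be ranked. Raising one drug while lowering the other gives a pair with no known toxicity order. 80/150 against 40/180 is the plainest case, because the Dose Level 1D text itself leads to it. 40/180 also stays a candidate after it is left, since the plan allows re-escalation to a level once declared not tolerated.

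The stake is that one set of DLT data can give two eliminated sets and two MTDs, depending on a ranking that the plan does not state and that would be chosen after the DLTs are known. Defining the MTD is a primary objective, and the MTD caps the RP2D.

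**Working it through.** **Inputs from the documents**
- Target DLT rate 25%; boundaries 0.197 and 0.298; Table B (Synopsis, Maximum Tolerated Dose; SAP 3.2.2, Table 2).
- Elimination if Pr(p > 0.25 | data) > 0.95 with at least 3 evaluable patients and a uniform prior (Synopsis).
- Early stop when at least 9 evaluable patients are at the current dose and the decision is to stay (step 3).
- First cohort: "The study will start at Dose Level 1 with up to 2 patients receiving 40 mg QD".

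**Assumed:** all DLT counts below, and an 80 mg level (a 100% rise from 40 mg, the top of the 50% to 100% range).

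**The plan's own figures.** With φ = 0.25, p1 = 0.6φ = 0.15 and p2 = 1.4φ = 0.35 (p1 and p2 are not stated and are assumed):
- λe = ln[(1−p1)/(1−φ)] / ln[φ(1−p1)/(p1(1−φ))] = ln(0.85/0.75) / ln(0.2125/0.1125) = 0.1968
- λd = ln[(1−φ)/(1−p2)] / ln[p2(1−φ)/(φ(1−p2))] = ln(0.75/0.65) / ln(0.2625/0.1625) = 0.2984

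Both match, and all 12 columns of Table B reproduce. The escalation arithmetic is sound.

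The operating-characteristics table in Protocol Appendix 6 lists six levels in one row. A one-dimensional six-level simulation was run with start at the second level, assumed cohorts of 3, a maximum of 36, a stop at 9 or more when the dose is retained, selection of the level closest to 25%, and 5000 runs. In the four scenarios shown it agrees within 1.3 points for selection, 0.3 points for allocation and 0.2 patients for mean size. Starting at the first level misses allocation by 10 to 12 points. The table thus behaves as a single ladder and does not test a two-drug grid.

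**Illustration (i), MTD, 14 patients.** Each step against Table B:
- 40/180: 2/2, step down (no elimination, as n < 3).
- 40/150: 0/3, raise RP-6306.
- 80/150: 1/4, 2/7 and 2/9, all stay; the stopping rule is met at 9.

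Pooled adjacent violators on raw rates:

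| Assumed ranking | Fitted rates in that order | MTD, 30% rule | MTD, <25% rule |
|---|---|---|---|
| 40/150 < 40/180 < 80/150 | 0, 4/11 = 0.364, 0.364 | 40/150 | 40/150 |
| 40/150 < 80/150 < 40/180 | 0, 2/9 = 0.222, 1.0 | 80/150 | 80/150 |

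The flip does not depend on which of the two MTD definitions is used, nor on raw-rate pooling. With rates (y + 0.05)/(n + 0.1) and inverse-variance weights, the fit at 80/150 is 0.749 under the first ranking and 0.225 under the second.

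**Illustration (ii), elimination, 8 patients.**
- 40/180: 1/2, step down. The posterior is Beta(2,2), so Pr(p > 0.25) = 0.844, and n < 3.
- 40/150: 0/3, raise RP-6306.
- 80/150: 3/3. The posterior is Beta(4,1), so Pr(p > 0.25) = 1 − 0.25⁴ = 0.996: eliminated, as Table B says.

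If 40/180 is ranked above 80/150, it is eliminated too, on two patients of its own. If ranked below, it stays open.

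**Under a two-drug partial order.** Only 40/150 ≤ 40/180 and 40/150 ≤ 80/150 are known. In (i) the raw rates 0, 1.0 and 0.222 violate neither relation, so the MTD is 80/150. In (ii), 80/150 and every combination at least as high in both drugs are removed, and 40/180 stays open. No ranking has to be chosen.

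**The case against.** **The sequence implies a ranking.** The text reaches 80/150 only after 40/180 has failed, which favours placing 80/150 below 40/180. That is a sensible reading, but it is an inference, and re-escalation leaves 40/180 in play. It is also the ranking under which illustration (ii) removes 40/180 on two patients.

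**The rule may stand elsewhere.** The public Protocol shows the synopsis and appendices, not the body sections that the SAP cites, and the plan points to drug-combination BOIN criteria and an online application. A two-drug order could be set out there, and this limits what can be said about the Protocol. It does not clear the SAP, whose step 2a gives no definition and whose section 7 names pooled adjacent violators.

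**The counts are chosen, and the RP2D rests on the totality of data.** Both are true. The illustrations show that a flip is possible, not that it is likely. The MTD does not pick the RP2D, but it bounds it.

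**Stronger readings the documents do not support.** A reader might infer that the sections contradict each other on which drug moves. They can be reconciled: the Module 1a step-down text can be read as the step size when RP-6306 is the drug moved, the Dose Level 1D and 2D text as a specific instruction that overrides the general rule, and footnote c leaves the order to SRC agreement. A reader might also build examples from 120/180, by stepping irinotecan down to 120/150 and then returning to 90/180 as the highest tolerated dose. That return raises irinotecan, which the RP-6306 sentence does not clearly permit, and calling it a step down already ranks 90/180 below 120/150.

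**Conclusion.** The point holds. The plan allows combinations that have no known toxicity order and applies elimination and MTD rules that need a complete one. In the examples, identical data give an MTD of 40/150 or 80/150, and 40/180 is removed or kept.

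This rests on assumed DLT counts and an assumed 80 mg level, on a path that the text permits. The frequency is not estimated and would depend on SRC choices. Nothing is affected while irinotecan stays at 180 mg/m² on one schedule, among combinations at one irinotecan dose, or among Dose Levels 1D to 3D at 40 mg, which are fully ordered. It would be wrong to infer that the BOIN boundaries are at fault or that any MTD from this trial is ambiguous. SRC freedom to choose between permitted neighbours is not the objection either; what is missing is the order used for elimination and for the final fit.

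**What to change.** 1. In the Protocol's overdose-control paragraph, and in step 2a of the Protocol and SAP 3.2.2, define a higher combination as one at least as high in both RP-6306 and FOLFIRI, within one RP-6306 schedule. The FOLFIRI order, from high to low, is irinotecan 180, 150, 120, then 120 without the fluorouracil bolus.
2. In the Protocol's MTD text, SAP 3.2.2 and SAP section 7, replace the one-dimensional fit and the highest-dose wording with isotonic regression on this partial order, using all DLT-evaluable patients on that schedule. State a tie-break for equal estimates, for example the lower RP-6306 dose.
3. Keep the hold of irinotecan at 150 or 120 mg/m² after intolerance, and leave the choice between permitted neighbours to the SRC.

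The cost is wording in both documents and a small partial-order routine, with no extra patients. There are two downsides. Slightly less information is borrowed across levels. Unordered combinations are no longer eliminated automatically, so the SRC must judge them on their own data. The tie-break is a convention, and the example given favours the lower RP-6306 dose.

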
Treatment-related Hematologic TEAEs:

- Grade 4 neutropenia lasting at least 7 days or if granulocyte colony-stimulating factor or granulocyte macrophage colony-stimulating factor is given at any time
- Febrile neutropenia (defined as absolute neutrophil count [ANC] <1000/mm³ with a single temperature of 38.3°C [101°F] or a sustained temperature of 38°C [100.4°F] for >1 hour)
- Grade 4 thrombocytopenia or Grade 3 thrombocytopenia associated with Grade ≥2 bleeding
- Grade 4 anemia or Grade 3 anemia requiring red blood cell (RBC) transfusion per local hospital guidelines

Note: The use of transfusions and hematopoietic growth factors, including thrombopoietin analogues, will be part of the DLT definition if such intervention is required.

Treatment-related Nonhematologic TEAEs:

- Grade ≥3 nausea/vomiting/diarrhea that lasts >3 days despite optimal supportive care
- Any Grade 3 treatment-related TEAE of >24-hour duration
- Any Grade 4 treatment-related TEAE of any duration

TEAEs That Will Not Be Considered a DLT Include the Following:

- Grade ≥3 nonhematologic laboratory abnormalities that are not considered clinically relevant in the opinion of the Investigator or respond to medical intervention
- Grade 3 fatigue with duration <7 days and resolved to Grade ≤2, unless it recurs within the first 2 cycles and is considered drug-related by the Investigator
- Grade ≥3 nausea/vomiting/diarrhea that has not been treated with optimal supportive care

Determination of Dose-Limiting Toxicities:

The population used for determination of DLTs will consist of patients who have met the minimum safety evaluation requirements of the study and/or who have experienced a DLT at any time during the initial 28 days of the study. Minimum safety requirements will be met if, during the first 2 cycles of treatment, the patient receives at least 75% of planned total doses of RP-6306 and 100% of the planned dose of FOLFIRI, completes all required safety evaluations per Schedule of Assessments, and is observed at least until 28 days following the first dose of study treatment.

If a patient withdraws from treatment during the first 2 cycles due to any reason other than DLT and does not meet the minimum requirements for inclusion in the DLT-determining population described above, that patient will be replaced.

Diagnosis and Main Criteria for Inclusion:

Inclusion Criteria:

- Written informed consent, according to local guidelines, signed and dated by the participating

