7.2. Treatment Exposure

Exposure will be derived for RP-6306 and FOLFIRI respectively.

Duration of Exposure for each drug RP6306 and FOLFIRI will be defined as the duration between the first and last doses of respective study drug

- Duration of RP6306 exposure = last dose date first dose date + 1.
- Duration of FOLFIRI exposure = last infusion date first infusion date + 14, due to 2 week infusion cycle

Overall duration of treatment for the study regimen is defined as Date of Treatment Discontinuation (from EOT page in the CRF) – first dose date +1. If treatment is still ongoing, use cut off date. If Date of Treatment Discontinuation is not collected, use the duration of exposure calculated above (take the longer of the either drugs)..

The last dose date will be obtained from the end of treatment (EOT) CRF page for each study drug. Number of days dosed will be derived as the number of days a patient received a dose of each study drug (i.e., excludes off treatment days and any missed doses).

Dose intensity for RP-6306 will be derived as:

Dose intensity = (total dose received/total planned dose)*100%

Total dose received (mg) for RP6306 is the sum of total doses (mg) received. If a patient had a dose reduction/change during treatment, then the total dose received will be calculated for each actual dose received and then summed to give the total dose received.

Total dose received: $\sum_{i=0}^{k}$ number of days dosed at dose $x_i * dose x_i$

for i = 1 to k where i represents the number of dose levels received and k = number of distinct dose levels

Total planned dose for RP6306 will be derived as initial assigned dose a patient will receive without any interruptions or reductions based on the time-period between the date of first dose and date of last dose after excluding days when dosing information is not available, accounting for the number of treatment days per week. This is assuming the days without dosing information is missing at random.

A dose interruption will be defined as a planned interruption where a decision is made to interrupt the dose temporarily, usually due to AE reason. Dose interruptions will be captured on the eCRF.

A dose reduction is any reduction prescribed by PI in dose/schedule compared to the initial dose.

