Patients who do not have an end of treatment date in the eCRF at the time of analysis and reporting will be considered ongoing treatment. For deriving exposure, ongoing patients will be assumed to be ongoing at the date of the data cut off and therefore the data cutoff date will be used to derive exposure.

Exposure for RP6306 will be listed and summarized by the Safety Population and presented by module 1a and 1b and dose/schedule.

The following will be presented for RP-6306 (if applicable)

- Duration of exposure (days)
- Number and % of patients with at least 1 cycle, with at least 2 cycles...etc (up to at least 5 cycles).
- Number of cycles treated (completed)
- Total dose received (mg)
- Dose intensity based on initial planned dose (%)
- Number and % of patients with at least one dose interruption reported in dosing log by considering only those incidences when AE is indicated as a reason
 - Further broken down by number with 1, 2 or \geq 3 interruptions
- Number and % of patients with at least one dose reduction (include dose reduction as a result
 of schedule change with less dose intensity) reported in dosing log considering only those
 incidences when AE is indicated as a reason
 - Further broken down by number with 1, 2 or \geq 3 reductions
- Number of patients with any dose escalation per protocol

Patients with both an interruption and reduction will be included in both the interruption and reduction summaries.

The following will be presented for FOLFIRI.

• Duration of exposure (days)

• Number of infusions received

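### SAP 7.2 reports FOLFIRI only as days and number of infusions, so the planned summaries cannot show how much of the backbone was delivered at each dose level or at the RP2D

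*Protocol*

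**What the plan says.** **What may be changed.** Footnote d to Table A in the protocol synopsis (repeated under SAP Table 1) is attached to the FOLFIRI rows of both modules: "Investigators that would like to hold or modify the administration of the fluorouracil bolus and/or leucovorin require approval" from the Medical Monitor. The available text sets no limit on cycle, reason or number of patients. Separately, the synopsis section on investigational product and dosage allows interruptions and reductions to manage toxicity, and does not restrict them to RP-6306.

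**How the plan treats the backbone elsewhere.** In the branch followed when Dose Level 1 is not tolerated, Level 3D differs from Level 2D only in the bolus: "dose Level 3D will be explored, in which the bolus of fluorouracil will be eliminated from the regimen". The BOIN rules count a change of backbone as a dose step: "1 level decrease of RP-6306 or 1 level decrease of FOLFIRI".

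**DLT evaluability.** In the first two cycles a patient without a DLT must be one who "receives at least 75% of planned total doses of RP-6306 and 100% of the planned dose of FOLFIRI". A patient with a DLT counts regardless.

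**Exposure reporting.** The synopsis text on safety lists exposure, with interruptions and modifications counted in, among the things by which safety and tolerability are judged. SAP 7.2 states "Dose intensity for RP-6306 will be derived as" a ratio of received to planned dose, and lists reductions, interruptions and escalations for that drug. For FOLFIRI it gives two items: a duration ("Duration of FOLFIRI exposure = last infusion date" minus first infusion date, plus 14) and "Number of infusions received".

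**Grouping.** SAP 5.1 presents safety and efficacy by assigned dose and schedule, and DLT rates by assigned initial level. SAP 4.4 presents all populations by initial dose received. SAP 7.1 assigns adverse events to the initial dose group after a modification.

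**The concern.** The primary objectives are the tolerability of the combination and its MTD and RP2D. A statement that a level was tolerable, or had a given response rate, is a statement about RP-6306 with a particular backbone. The plan itself treats backbone changes as dose steps, and it lets individual patients depart from the level's backbone. The planned FOLFIRI summary does not change when they do. A reader of the study report could then not tell whether a level's safety and efficacy results came from full FOLFIRI or from a mixture, and could not tell how large the reduced share was. This matters most after Cycle 2, where no evaluability rule applies and where most of the efficacy follow-up lies.

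**Working it through.** **1. The plan's own design figures.** With target 0.25 and the usual default limits 0.6 × 0.25 = 0.15 and 1.4 × 0.25 = 0.35 (multipliers assumed):

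- Escalation boundary = ln(0.85/0.75) / ln[(0.25 × 0.85)/(0.15 × 0.75)] = 0.1968; the protocol states 0.197.
- De-escalation boundary = ln(0.75/0.65) / ln[(0.35 × 0.75)/(0.25 × 0.65)] = 0.2984; the protocol states 0.298.

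The escalate, de-escalate and eliminate rows of Table B also reproduce for 1 to 12 patients. The design table is not at issue.

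**2. What the FOLFIRI summary can and cannot see.** Component doses are from Table A: bolus 400 mg/m² and infusion 2400 mg/m², so 2800 mg/m² fluorouracil per cycle. The bolus share is 400/2800 = 14.3%. Take two patients with four cycles on schedule, counting one infusion per cycle (the SAP does not define the count):

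| | Full backbone | Bolus held throughout |
|---|---|---|
| Duration, SAP 7.2 | 42 + 14 = 56 days | 56 days |
| Number of infusions | 4 | 4 |
| Fluorouracil received | 4 × 2800 = 11,200 mg/m² | 4 × 2400 = 9,600 mg/m² |
| Relative dose intensity, fluorouracil | 100% | 85.7% |

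Holding leucovorin in all four cycles would give 0% for that component, again with 56 days and 4 infusions. Footnote d does not cover irinotecan, but the general allowance for toxicity reductions can. The size of such reductions is not in the available text. Using Table A's own levels as an illustration, 150/180 = 83.3% and 120/180 = 66.7%, and neither changes the two reported items. Duration and count together hint at delays, but they say nothing about reductions or omissions.

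**3. Other outputs that might fill the gap.** SAP 7.1 tabulates and lists adverse events leading to dose modification of study treatment, and SAP 5.2.1 puts all recorded data in listings. The first misses holds not caused by an adverse event, and neither gives component dose intensity by level. SAP 6.1 does not treat changes for AE management as treatment deviations, and an approved hold is not clearly an incorrect dose.

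**4. The MTD under each reading of *planned*.** The documents give no DLT rate with and without the bolus and no frequency of holds, so the rates below are assumptions.

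*(a) Planned means the approved, modified dose.* Held patients without a DLT count at the full level. At six patients, Table B escalates with at most 1 DLT. With true rates 0.35 (full) and 0.20 (held), the exact chance of escalation is 0.319, 0.366, 0.417 and 0.473 with 0, 1, 2 and 3 held. Over full 0.30-0.40 and held 0.15-0.25, it is 0.36 to 0.59 with 3 held, against 0.23 to 0.42 with none.

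*(b) Planned means the level's regimen.* Held patients count only if they have a DLT. With a true rate of 0.25 in everyone and a fraction h held, the counted rate tends to 0.25 / [0.25 + 0.75 × (1 − h)]:

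- h = 1/6: 0.25/0.875 = 0.286
- h = 2/6: 0.25/0.750 = 0.333
- h = 3/6: 0.25/0.625 = 0.400

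Replacing non-evaluable patients does not remove this, because the replacements follow the same rule. The two readings push the DLT rate in opposite directions.

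**The case against.** A reader might infer that a level could be declared tolerated with full FOLFIRI only because the bolus was dropped, so that the MTD is credited to a backbone not given. The documents do not support that as stated. Evaluability asks for 75% of RP-6306 but 100% of FOLFIRI, and the ordinary sense of planned is the assigned regimen. SAP 7.2 defines planned dose for RP-6306 in that sense, as the initial assignment before any interruption or reduction. That definition is not written for FOLFIRI, so it is strong context rather than proof. On this reading a held patient without a DLT never supports escalation.

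A reader might also see a contradiction between footnote d and Level 3D. Level 3D exists only in the branch after Level 1 fails, at 40 mg RP-6306, and a cohort step can coexist with an approved individual hold. The passages need reconciling, but they do not exclude each other.

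The AE-driven tables and the listings would show part of what is missing, the RP2D rests on the totality of the data, and only the synopsis and appendices of the protocol are available. Body text on FOLFIRI modification, or Section 11.1, to which the SAP refers for the DLT population, may say more.

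All of this limits the MTD argument. It does not answer the reporting gap: the FOLFIRI items in SAP 7.2 are explicit, and none of the other outputs gives the backbone delivered by dose level.

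**Conclusion.** The reporting gap stands. In a trial whose primary objectives concern a combination, the planned exposure tables describe delivery of one partner and only the time course of the other. With the bolus held, 14% of the fluorouracil per cycle can be missing without changing duration or the per-cycle infusion count. Leucovorin can be missing entirely, and irinotecan can be reduced, with the same result. This affects the reading of safety and efficacy by level and at the RP2D, and any modification after Cycle 2.

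The effect on the MTD is conditional. It depends on a word not defined for FOLFIRI in the available text. On the more natural reading, held patients without a DLT are already excluded, and the remaining distortion is upward. The sizes in step 4 rest on assumed DLT rates and assumed numbers of holds, and show direction and scale only. That one infusion is counted per cycle is also an assumption.

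**What to change.** **In SAP 7.2**, add for irinotecan, leucovorin, fluorouracil bolus and fluorouracil infusion, by module and dose level: relative dose intensity against the assigned level, and n (%) of patients with a reduction, an omission or a delay. State what counts as one infusion.

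**In the DLT and response listings**, flag every patient with a modified backbone, with the component and the cycle.

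**For the DLT rate**, add a sensitivity summary by level that leaves out all patients with a modified backbone in Cycles 1-2, whether or not they had a DLT. Dropping only those without a DLT would produce the upward distortion in step 4(b). For this summary, a change made because of a DLT should not itself count as a modification; otherwise DLT patients would be removed selectively.

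**Reconciliation by the sponsor.** Footnote d, Level 3D and the evaluability wording (protocol synopsis, SAP 3.3 and 4.1) should be read together, and the text should state what planned means for FOLFIRI after an approved hold. No dose or clinical rule is proposed here.

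**Cost.** SAP wording and a little extra programming, assuming that component doses are recorded in the eCRF, which is not among the documents. The sensitivity summary will rest on few patients per level and should be read as descriptive.
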